- The patient is a candidate for loco-regional radiation therapy according to national or institutional guidelines. In Denmark DBCG guidelines must be followed, thus axillary lymph node status (FNA or SN positive macrometastatic nodes) gives indication for regional nodes radiation therapy to levels (I), II, III, IV, interpectoral nodes and the internal mammary nodes (IMN).
- Highly selected patients with inflammatory breast cancer, namely those with complete or near complete response to neoadjuvant systemic therapy judged by imaging and clinical examination before surgery. Any skin edema and clinical signs of skin involvement must have disappeared during systemic therapy. It is highly recommended that the decision to offer an inflammatory breast cancer patient inclusion in the DBCG RT Recon trial is made during a multidisciplinary team conference.
- Adjuvant systemic therapy with chemotherapy, endocrine therapy, anti-HER2 treatment and other targeted therapies used in the adjuvant setting either as new standard or as part of a trial during the course of the trial is accepted.
- Neoadjuvant chemotherapy and primary systemic therapy of an operable breast cancer is accepted.
- Patient with previous non-breast malignancy is accepted if the patient has been without disease minimum 5 years, and the treating oncologist estimates a low risk of recurrence. Patients with the following diseases can be accepted despite less than 5 years disease free interval: carcinoma in situ cervicis, carcinoma in situ coli, melanoma in situ, basal cell carcinoma of the skin, squamous cell carcinoma of the skin.
- Life expectancy minimum 10 years.

Exclusion criteria

- Pregnant or lactating.
- Previous breast cancer or DCIS.
- Bilateral breast cancer.
- Previous radiation therapy to the chest region.
- Previous non-breast malignancy (not including carcinoma in situ of the cervix or colon, melanoma in situ, basal cell carcinoma of the skin, and squamous cell carcinoma of the skin) within 5 years.
- Conditions indicating that the patient cannot go through breast reconstruction, the radiation therapy or follow up.
- Not being able to participate due to language or other personal issues.
- Life expectancy less than 10 years.

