The patient can be included irrespective of the type and timing of systemic therapy. This trial accepts that randomized patients participate in other trial protocols testing new systemic therapies, e.g. inhibitors of CDK4 and CDK6 kinase activity like abemaciclib in the Monarch E trial. It is also accepted that the patient is included in trials testing loco-regional therapies, e.g. the SENOMAC trial and the

Skagen Trial 1.

TREATMENT PROTOCOL

The first version of the trial was designed as a randomized trial. The inclusion started 1/1-2020. Due to slow accrual, the steering committee has decided to change the trial per 30/6-2023 to a prospective trial of arm A without randomization. It is expected that a prospective trial design will make it feasible for more departments to participate

Treatment arm A

Delayed-immediate reconstruction:

Primary Surgery: Skin sparing mastectomy (nipple sparing if appropriate) and axillary surgery according to guidelines or protocol. Reconstruction with silicone implant or expander covered by pectoral muscle and mesh or matrix.

Delayed reconstruction: Final reconstruction with any reconstructive procedure – being it autologous or implant-based (one- or two-stage, +/- acellular dermal matrix (ADM)) – is performed 6-12 months after completion of chemotherapy and RT. Any contralateral procedure is allowed when doing the delayed surgery, but not in relation to the initial cancer surgery.

Patients, who will not have the second delayed procedure performed will be included in the analysis of 'intention to treat' group and not excluded from the study.

Treatment arm B

Delayed reconstruction:

Primary surgery: Total mastectomy and axillary surgery according to guidelines or protocol.

Delayed reconstruction: 6-12 months after completion of PMRT: final reconstruction with any reconstructive procedure – being it autologous or implant-based (one-or two-stage, +/- ADM). Any contralateral procedure is allowed at any time point after PMRT has been delivered.

This arm recruited patients between 1/1-2020 and 30/6-2023

Concerning post mastectomy radiation therapy (PMRT)

This issue is described in the new ESTRO consensus guidelines for target volume delineation in implant based reconstruction ²⁶.

In general, the tissue beneath the skin surface of the mammarian region is the clinical target volume in all cases.

Implant-based reconstruction and PMRT

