Is measured at abduction/flexion with the patient sitting in front of a poster with a circle with degrees 0-180° (Appendix X).

Capsular contracture

Capsular contracture is measured by Bakers Grading (Appendix X)

Objective evaluation will be done at follow-up before and 1 year after first surgery and at year ½,1,2,3,4,5, and 10 after second operation and stored in the DBCG database under RECON follow-up.

Photos

Frontal and side-photos pre-operatively with arms down and arms up, before first surgery, after first surgery but before start of radiation therapy, and at year 1, 2, 3, 4, 5, and 10. At any event new photos are taken.

The photos will be stored in a database established for that purpose at Aarhus University Hospital.

The guidelines for photos is in Appendix XI.

BREAST-Q and QoL-questionnaires

TREATMENT ARM A/Prospective study	PRE-OP	POSTOP	POST-OP	POST-FINAL
Delayed-immediate INSTRUMENT		2 WEEKS	9-15 MO (pre-final recon) ###	RECON $\frac{1}{2}+1+2+3+4+5+10$ YEARS
DBCRT Recon Questionnaire*	X	X	X	X
BREAST Q** Part I_B	X		X	
BREAST Q Recon ** Part II_B		X	X	X
BDI Becks Depression Inventory**	X	X	X	X
CARQ-3 Concerns About Recurrence Questionnaire -3**	X	X	X	X

* Mandatory Questionnaires

**Optional Questionnaires for Danish patients only. Data can be stored in RedCap

If the patient does not undergo a final reconstruction, they will have the same POST-FINAL RECONS-questionnaires as the ones who do and at the same time-points, but will not have the PRE-FINAL RECON-questionnaire.

TREATMENT ARM B Delayed reconstruction INSTRUMENT	PRE-OP	POSTOP 2 WEEKS	POST-OP 9-15 MO (pre-final recon)	POST-FINAL RECON ½+1+2+3+4+5+10 YEARS
DBCG RT Recon Questionnaire*	X	X	X	X
BREAST Q** Part I_A	X			
BREAST Q** Part II_A		X		
BREAST-Q** Part I_B			X	
BREAST-Q** Part II_B				X
BDI Becks Depression Inven- tory**	X	X	X	X
CARQ-3 Concerns About Recurrence Questionnaire -3**	X	X	X	X

* Mandatory Questionnaires

**Optional Questionnaires for Danish patients only. Data can be stored in RedCap

STATISTICAL CONSIDERATIONS

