During the active RCT it was found that some of the included patients did not wish for the delayed (autologous) reconstruction, but rather kept their primary implant. It therefore seems that the rate of capsular contracture is lower than originally expected, perhaps due to a more gentle radiation therapy in the protocol.

For the prospective study, all participants will be included in the analyses, but stratification for type of final reconstruction will be performed.

ETHICAL CONSIDERATIONS

This trial is being conducted according to the 5th version of the Helsinki Declaration. The trial can only start after the approval of the regional ethical committee for Region Midt.

The risk of complications and failure is increased in breast reconstruction after mastectomy in patients who have RT. This is well known but still more and more patients request and receive such procedures.

Patients participating in the present study will be informed that reconstruction combined with RT doubles the risk of complications no matter which treatment arm they belong to. Presumably, delayed-immediate reconstruction will lead to better results and a higher satisfaction to the patients than will delayed, secondary reconstruction if patients have a uncomplicated trajectory. Therefore, if delayed-immediate reconstruction can be performed without increasing other risks, it could turn out to be preferable, and that is what the present study aims to prove.

At present there is no firm evidence and no consensus on which procedure to preferre, but there is an international trend towards primary reconstruction also in this group of patients, and there is a risk that this approach will be routinely adopted before sufficient evidence is available, for which reason it is crucial to first explore this option through a study.

PUBLICATIONS

The results from this study will be published irrespective them being positive, negative, or inconclusive. After approval of the study from the local scientific committee, the study will be registered on www.clinicaltrials.gov according to current recommendations.

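### The one objective examination between the two operations is not tied to the second operation and may fall after it, and women who keep their implant have no dated objective visits after year 1

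*Protocol*

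**What the plan says.** Under REGISTRATION, the protocol describes three objective measures: arm circumference for lymphedema, shoulder range of motion, and contracture ("Capsular contracture is measured by Bakers Grading (Appendix X"). They share one schedule: "Objective evaluation will be done at follow-up before and 1 year after first surgery", followed by visits at ½, 1, 2, 3, 4, 5 and 10 years counted from the second operation. All three are secondary morbidity endpoints under OUTCOME.

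The questionnaire tables that follow have a different time point between the operations, "9-15 MO (pre-final recon", in both arms. A note to the arm A table says that women without a final reconstruction receive the post-final questionnaires at the same times as the others and skip the pre-final one. There is no such note for the objective evaluation.

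Under TREATMENT PROTOCOL, the arm A final procedure "is performed 6-12 months after completion of chemotherapy and RT". It may be of any kind: "Final reconstruction with any reconstructive procedure – being it autologous or implant-based". In arm B it comes 6-12 months after the end of radiotherapy. The inclusion criteria add: "Neoadjuvant chemotherapy and primary systemic therapy of an operable breast cancer is accepted".

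STATISTICAL CONSIDERATIONS reports that some women in the randomised period kept their primary implant. It keeps all participants in the analyses, with stratification by type of final reconstruction.

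**The concern.** In arm A, contracture of the irradiated first implant can be graded only while that implant is in place. The final procedure may remove or replace it. An examination fixed by calendar time from the first operation does not guarantee a grade before that happens. If the second operation comes first, the one-year visit records the state of the breast after it, and the next objective visit is half a year after the second operation. The set of one-year values then mixes findings before and after the second operation. Shoulder motion and arm circumference are mixed in the same way, and for these arm B is affected too.

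The second part concerns women who never have a second operation. Every objective visit after year 1 is counted from an event that does not occur for them. They carry an irradiated implant in the long term, and the protocol intends to follow morbidity for 10 years and to revisit the national recommendation if later results differ.

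An analysis plan can separate grades taken before and after the second operation. It cannot supply a grade that was never taken.

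**Working it through.** The protocol states no figure on this point, so there is none to reproduce. The check is interval arithmetic on its own windows.

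**Inputs**

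- Objective examination: month 12 after first surgery (REGISTRATION).
- Second operation in arm A: 6-12 months after chemotherapy and radiotherapy are complete (TREATMENT PROTOCOL).
- T, the months from first surgery to the end of that therapy: not given. Assumed range 2 to 8. Chemotherapy before surgery shortens T, and chemotherapy after surgery lengthens it.
- Spread of operations within the 6-12 month window: not given. Assumed even.

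**Is a second operation before month 12 permitted?** The earliest date is T + 6, which lies before month 12 whenever T is below 6. Chemotherapy before surgery is accepted, and nothing in the protocol rules out such values of T.

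**What share would precede the examination?** With an even spread from T + 6 to T + 12, the share before month 12 is (12 − (T + 6)) / 6 = (6 − T) / 6, and zero for T of 6 or more.

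| T (months) | Window for second operation (months) | Share before month 12 |
|---|---|---|
| 2 | 8-14 | 4/6 = 67% |
| 3 | 9-15 | 3/6 = 50% |
| 4 | 10-16 | 2/6 = 33% |
| 5 | 11-17 | 1/6 = 17% |
| 6 | 12-18 | 0% |
| 7 or 8 | 13-19 or 14-20 | 0% |

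These are shares of women who have a second operation. If a fraction k keep the first implant, the share of all arm A women is the table value times (1 − k). The protocol gives no value for k.

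**A reference point in the protocol.** The introduction cites a ten-year series with final reconstruction about 12 months after the primary operation and 7 months after radiotherapy. That puts the end of radiotherapy near month 12 − 7 = 5, the 17% row. The series places typical operations close to the examination date, but it does not give the dates in this trial.

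**Women without a second operation.** Their objective visits before first surgery and at one year are defined. The visits at ½, 1, 2, 3, 4, 5 and 10 years have no starting date. The questionnaire note does not supply one, because its time points are also counted from the final reconstruction.

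**The case against.** The strongest reply is that both schedules describe one visit. The 9-15 month window is 12 months plus or minus 3, and the later time points are identical in both schedules, so one year could be the nominal date of the pre-final visit. That reading is possible, but the text does not state it, and a site following the text literally would examine at 12 months whether or not the second operation had taken place.

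It can also be said that a fixed one-year examination is a legitimate choice for lymphedema and shoulder motion, and that the protocol does not define the endpoint as contracture of the first implant before the second operation. Both are fair. Neither helps if the grade of the irradiated implant is wanted later.

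Three stronger readings are tempting and are not supported.

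- A reader might infer from 9-15 months that about half of the women are examined too late. That window dates a questionnaire given before the operation, not the operation itself. The 50% arises only at T = 3 with an even spread.
- A reader might infer that the contracture rate is biased downwards, because women with severe contracture may be operated on earlier. This is plausible, but the documents give neither contracture rates nor operation dates by grade, and women who keep their implant have a valid one-year grade.
- A reader might take the remark "It therefore seems that the rate of capsular contracture is lower than originally expected" as a product of this schedule. The protocol draws it from women declining the delayed procedure and cites no Baker grades.

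**Conclusion.** The point holds as a gap in the visit schedule. The only objective examination between the operations is not anchored to the second one, the protocol's timing rule permits the second one first, and for such a woman no grade of the irradiated first implant is scheduled. Separately, and with no assumption needed, women without a second operation have no dated objective follow-up after year 1.

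Among women who have a second operation, the share affected lies between 0% and about 67% for T from 6 or more down to 2 months, given an even spread of operations over the permitted window. The protocol does not allow a narrower range, and neither the size nor the direction of any bias can be derived from it.

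The primary endpoint is untouched. The contracture part is limited to arm A, because arm B has no implant between its operations. This is an improvement worth making at small cost, not a threat to the main conclusion.

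**What to change.** Amend the objective evaluation schedule under REGISTRATION in three places.

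1. Hold the existing examination between the operations as the pre-final visit, always before the second operation: at one year after first surgery or just before the second operation, whichever comes first. State how it relates to the 9-15 month questionnaire window.
2. For women without a second operation, keep the one-year examination and count later objective visits from a stated date, such as that visit. Use the same date for their questionnaires, which now lack one, and say how visits are counted if a second operation takes place later.
3. Report contracture of the first implant from this examination before the second operation.

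For women with a second operation, one examination moves and none is added. The price is that time since first surgery varies at this visit. The earliest permitted operation is at month T + 6, so the visit can be up to 12 − (T + 6) = 6 − T months early, for example 4 months at T = 2 or 3 months at T = 3. Recording the actual examination date lets the analysis take this into account. Contracture that appears between month 12 and a later second operation would still be missed, as it is now.

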In the setting of post-mastectomy radiation therapy (PMRT), or any other adjuvant therapy for that matter, it is of utmost importance to choose the safest reconstructive technique in order not to delay adjuvant therapy^{17,18}. This favors a surgical procedure with no donor-site and a simple reconstruction. Several studies on timing of radiation therapy and reconstructive procedures have been published including 3 reviews.¹⁹⁻²¹ These papers systematically review the currently available evidence, describing in-coherent, retrospective, smaller or larger cohorts of patients from multiple centers, who had either implant-based or autologous reconstructions performed on very different time-points in the course of treatment.¹⁹ The patients had, moreover, undergone various radiation protocols (different doses, with or without boost and bolus etc.). In addition, different outcomes are reported in the individual studies, and it is therefore not possible to draw any firm conclusion on which type of reconstructive procedure to prefer

Very recently published studies likewise do not give a clear indication on which type of reconstruction to prefer in patients undergoing radiation therapy as well,²²⁻²⁴ although one of the studies reports acceptable results with autologous immediate breast reconstruction.²³ The long-term oncological outcome after reconstruction and radiation therapy is not well described, but recently the 10-year experience with delayed immediate reconstruction at MD Anderson Cancer Center was published.²⁵ Almost 400 patients were treated with skin-sparing mastectomy and immediate tissue expander placement and subsequent radiation thera-

py. Final reconstruction was performed around 12 months after the primary operation and 7 months after PMRT. Eighty-five percent had a final procedure performed. Thirteen percent had complications and had the expander removed. Five-years loco-regional control and overall survival was 99% and 92%, respectively. Data on target volume definition and radiation therapy technique used as well as cosmetic outcome in this patient cohort are still awaited.

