At the first consultation and in the written information about the trial the patient is informed that we want information from her patient file passed on to the trial regarding tumour characteristics, and also about her recurrence and survival status for 15 years after randomization and on events related to the reconstruction. If she has a recurrence we need data passed on from her patient file regarding when and where the recurrence took place. The tumour characteristics are: tumour histological type, size, lymph node status (how many removed and how many with metastasis and what type of metastasis), malignancy grade/ER/PR/HER2/Ki67 status, Q score, resection margin, and surgical procedure, radiation therapy, and systemic treatment. Also information about serious events like a new cancer, heart disease, lung disease and stroke is passed on from her patient file, because these events may be related to the radiation therapy. If an increased risk of any of these events is associated with one of the radiation therapies on trial, it will influence the decision on what is to be future standard therapy.

The patient will be informed that the consent provides the investigators of the study direct access to obtain the necessary information from medical records to conduct the investigation and follow-up.

OUTCOME

Primary endpoint

Any complication deeming *surgical intervention* necessary (excluding percutaneous drainage and antibiotic treatment for inflammation in cases without need for open drainage) within a period up to 1 year after the final reconstruction:

- Infection
- Hematoma
- Loss of implant/expander
- Necrosis
- Seroma

Secondary endpoints

- Necrosis not requiring surgical intervention
- Infection not requiring surgical intervention but antibiotic treatment
- Herniation at donor-site
- Patient's satisfaction and QoL evaluated by BREAST-Q – appropriate modules.
- Psycho-oncological endpoints evaluated by validated questionnaires:
 - Depression (Becks Depression Inventory, BDI)
 - Fear of cancer recurrence (Concerns About Recurrence

Questionnaire-3, CARQ-3)

- Timely initiation of adjuvant therapy
- Morbidity including lymphedema, capsular contracture and range of motion (ROM) of the shoulder
- Breast photos
- Recurrence
 - Local recurrence
 - Regional recurrence
 - Distant metastasis
 - Disease-specific survival
 - Overall survival
- Death including cause of death

Concerning cancer related endpoints

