APPENDIX

IIa	DBCG RT RECON Primary endpoints after first surgery
IIb	DBCG RT RECON Primary endpoints after second surgery
III	BDI Becks Depression Inventory
IV	CARQ-3 Concerns About Recurrence Questionnaire-3
V	Breast-Q Part I_A Questionnaire before mastectomy
VI	Breast-Q Part I_B Questionnaire before reconstruction
VII	Breast-Q Part II_A Questionnaire after mastectomy
VIII	Breast-Q Part II-B Questionnaire after reconstruction
IX	DBCG RT RECON Questionnaire (morbidity)
X	DBCG RT RECON Registration form (morbidity and cosmesis)
XI	DBCG RT RECON Manual for clinical photos

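### Arm A women who end with no reconstructed breast are assigned the after-reconstruction BREAST-Q (Part II_B) at every post-final visit, although the protocol holds an after-mastectomy form

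*Protocol*

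**What the plan says.** The secondary endpoints include "Patient's satisfaction and QoL evaluated by BREAST-Q – appropriate modules". Which module is used is fixed later, in the two schedules under BREAST-Q and QoL-questionnaires.

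- **Arm A and the prospective study.** Part I_B is given before surgery and at 9–15 months. Part II_B is given at 2 weeks, at 9–15 months and at ½, 1, 2, 3, 4, 5 and 10 years after final reconstruction. Part II_A does not appear.
- **Arm B.** Part I_A is given before surgery, Part II_A at 2 weeks, Part I_B at 9–15 months and Part II_B after final reconstruction.
- **Note under the arm A schedule.** "If the patient does not undergo a final reconstruction, they will have the same POST-FINAL RECONS-questionnaires as the ones who do", at the same time-points. The sentence goes on to withdraw the pre-final questionnaire from these women.
- **Appendix list.** The two postoperative forms are "Breast-Q Part II-B Questionnaire after reconstruction" and "Breast-Q Part II_A Questionnaire after mastectomy".

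Under Treatment arm A, "Patients, who will not have the second delayed procedure performed will be included in the analysis of 'intention to treat' group". The end of Statistical Considerations reports that some women in the randomised phase preferred to keep their primary implant.

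**The concern.** The note treats women without a final reconstruction as one group, but they are in at least two different states. A woman who keeps her primary implant has a reconstructed breast, and a form written for use after reconstruction fits her. A woman whose implant or expander was removed and who had nothing further has a mastectomy and no reconstructed breast. Both receive Part II_B for ten years.

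The second group is foreseen: "Loss of implant/expander" is a component of the primary endpoint, and women without the second procedure stay in the analysis. These women have had one of the poorest surgical results, and they are the ones whose satisfaction data are least secure. The Aim section names patient-reported outcomes, compared with preoperative measurements, as part of the trial's purpose. The choice of form is a data-collection decision, so an analysis plan cannot recover answers that were never asked for.

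**Working it through.** **1. Which form each state of the breast receives, from the schedules and the note.**

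| Woman's state | Arm | BREAST-Q form |
|---|---|---|
| Mastectomy only, 2 weeks after surgery | B | Part II_A |
| Final reconstruction done | A or B | Part II_B |
| No final reconstruction, primary implant kept | A | Part II_B |
| No final reconstruction, implant or expander lost | A | Part II_B |
| Never reconstructed | B | No rule stated |

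The first and fourth rows describe the same anatomical state, a mastectomy with no reconstructed breast, but different forms are assigned. This is the inconsistency. It rests on the form titles and the protocol's own use of them, because the item content is not in the document.

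**2. The 9–15 month visit.** That column is labelled as pre-final reconstruction. The note withdraws the pre-final questionnaire from women without a final reconstruction, so Part I_B at 9–15 months does not fill the gap. On a literal reading, Part II_B is the only BREAST-Q form they receive after surgery.

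**3. The planned number.** Statistical Considerations gives 178 patients for a one-sided exact test at 2.5%, success 0.74 against a limit of 0.64, power 80%. At n = 178 the smallest critical value with P(X ≥ r | 0.64) ≤ 0.025 is r = 127. This gives a type 1 error of 0.0233 and power at 0.74 of 0.815. The figure reproduces and is used below only to set the scale.

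**4. Size of the group.** The rates come from studies the protocol cites; applying them to this trial is an assumption.

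- No final procedure in the cited delayed-immediate series (introduction): 100% − 85% = 15%; 0.15 × 178 = 26.7, about 27 women.
- Expander removal in the same series, "Thirteen percent had complications and had the expander removed": 0.13 × 178 = 23.1, about 23 women.
- Implant loss with radiotherapy in the register study (Risk to the Patient), 21.9%: 0.219 × 178 = 39.0, about 39 women.

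The affected women are those who both lost the device and had no final reconstruction. The overlap is not reported, but it cannot exceed the number without a final procedure. On the 15% figure the group is therefore 0 to about 27. If the same series' 13% removal rate is also taken as a ceiling, the upper end is about 23. The number with BREAST-Q data will be smaller still wherever patients are not Danish or decline the optional forms.

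**The case against.** **A single form for everyone is defensible.** It keeps one instrument across the intention-to-treat group and avoids making the instrument depend on outcome. By title, Part II_B pairs with Part I_B, which is arm A's preoperative form. Part II_A pairs with Part I_A, which arm A never completes. This stands as a real cost of changing the rule. It does not make a form for use after reconstruction fit a woman who has none.

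**The misfit is inferred from titles.** This is true. If the two forms share scales, these women could still answer the shared part of Part II_B and would not be lost entirely. So the claim must be that scores may be missing or uninterpretable, not that they will be.

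**The protocol already has flexibility.** The endpoint speaks of appropriate modules, and analyses are to be stratified by type of final reconstruction. But the schedule and note are the specific rule, and they name one form. Because implant loss is recorded, kept and lost implants could be separated at analysis, but stratification cannot supply answers to a form that was not given.

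**The impact is limited.** BREAST-Q is secondary, optional and for Danish patients only. The same women still receive the mandatory morbidity questionnaire and are scheduled for the depression and fear-of-recurrence instruments. This stands.

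**Stronger readings that the document does not support.**

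- A reader might infer that long-term satisfaction is valid only in women whose first reconstruction survived. That is too broad: a woman who loses her implant and is later reconstructed can complete Part II_B.
- A reader might infer that reported satisfaction will be inflated by a few points. If the share missing were 5–13% and their satisfaction 20–30 points lower, the mean would be too high by 0.05 × 20 = 1.0 to 0.13 × 30 = 3.9 points. The 5% and the 20–30 points have no source in the protocol. The 13% counts removals, not women left without a breast. If these women answer and score low, the mean is not inflated at all.
- A reader might infer that the protocol presumes higher satisfaction for all women in arm A. Ethical Considerations presumes it only for those with an uncomplicated course, which excludes women with implant loss.

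**Conclusion.** The concern holds for a defined group: arm A women who lost the implant or expander and have no reconstructed breast at a post-final visit. For them the note fixes a form that, by its title and by the protocol's own practice in arm B, does not match their state, and it also removes their 9–15 month form. On the cited 15% without a final procedure, the group is 0 to about 27 of 178; its actual size is not given. Neither the size nor the direction of any bias in the satisfaction endpoint can be computed from the document. The primary endpoint and the sample size are untouched. The change is worth making because data missed at these visits cannot be recovered later.

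**What to change.** Rewrite the note under the arm A schedule so that the form follows the state of the breast:

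- Record at each post-final visit whether an implant, expander or flap is present, or none.
- Give Part II_B (Appendix VIII) to women with a reconstructed breast and Part II_A (Appendix VII) to women with none.
- State the same rule for arm B women who are never reconstructed, for whom there is now no rule.
- Report satisfaction together with the number of women who had no reconstructed breast, and pool all women only on scales that prove common to both forms.

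The effort is a short change to the note, one status item and a branching rule in REDCap. Both forms are already appended.

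The change has two costs. Scales found only in Part II_B will be unavailable for these women. Arm A also has no Part I_A baseline to pair with Part II_A, so their change from baseline is limited to any shared scales. The form will depend on outcome, which the report should say openly.
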